5.2. TREATMENT PATTERN ENDPOINT(S)

Variable	Operational definition
Treatment Regimen Duration	Months from the start date to the end date of a treatment regimen. For ongoing regimen, the end date is the data cutoff date.
Treatment Sequence Duration	Months from the start date of the first treatment regimen to the end date of the last treatment regimen within the same line of therapy. For ongoing regimen, the end date is the data cutoff date. This will be calculated for up to 3 lines of therapy.
The following dosing information will be presented for palbociclib, CCI	
Start dose	Start dose level of palbociclib, CCI
End dose	End dose level of palbociclib, CCI
Duration of Treatment	Months from the start date to the end date of the treatment. For ongoing treatment, the end date is the data cutoff date.
Reason for Discontinuing Treatment	Cost; Disease Progression; Patient Refusal/Request; Toxicity, specify; Death, Other, specify, Undocumented
Time to Dose Discontinuation	Months from the start date to the discontinuation date of the treatment.
Type of Dose Adjustments	Dose Modification; Schedule Changes; Dose Delay; Hold; Discontinuation
Time to First Dose Adjustment	Months from the start date to the first adjustment date of the treatment.

PFIZER CONFIDENTIAL

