6. HANDLING OF MISSING VALUES

No imputation for missing values will be performed.

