^d Visceral: metastasis at one or more of the following sites: liver, pancreas, intestines, lung, heart, malignant pleural effusion, peritoneum, pleura. Other metastasis sites, including bone or non-visceral metastasis, may be present.

^e Non-visceral: metastasis at one or more of the following sites: bone, brain, skin, chest wall, contralateral breast, or distant lymph nodes.

^f Bone only: Bone metastasis, with no metastasis at any other identified site.

Table 2b. Summary of Clinical Characteristics – Palbociclib + AI Patients

Repeat Table 2a for patients receiving Palbociclib with AI as initial endocrine-based therapy.

CCI

Table 3a. Summary of Treatment Regimen Duration – All Eligible Patients

		Treatment Regimen Duration (months)				
		n	%	Mean	SD	Median
Line 1	Regimenx	XXX	XXX	XXX	XXX	XXX
	Regimeny	XXX	XXX	XXX	XXX	XXX
	Regimenz	XXX	XXX	XXX	XXX	XXX
	...	XXX	XXX	XXX	XXX	XXX
Line 2	Regimenx	XXX	XXX	XXX	XXX	XXX
	Regimeny	XXX	XXX	XXX	XXX	XXX
	Regimenz	XXX	XXX	XXX	XXX	XXX
	...	XXX	XXX	XXX	XXX	XXX
Line 3	Regimenx	XXX	XXX	XXX	XXX	XXX
	Regimeny	XXX	XXX	XXX	XXX	XXX
	Regimenz	XXX	XXX	XXX	XXX	XXX
	...	XXX	XXX	XXX	XXX	XXX

Lines of therapy are progression-based and are restricted to the first 3 lines.

Table 3b. Summary of Treatment Regimen Duration – Palbociclib + AI Patients

Repeat Table 3a for patients receiving Palbociclib with AI as initial endocrine-based therapy.

[figure not shown]
CCI

Table 4a. Summary of Treatment Sequencing Duration – All Eligible Patients

	Treatment Sequence	Duration (month)				
		n	%	Mean	SD	Median
One line	Line 1 Regimenx	XXX	XXX	XXX	XXX	XXX
	Line 1 Regimeny	XXX	XXX	XXX	XXX	XXX
	Line 1 Regimenz	XXX	XXX	XXX	XXX	XXX
	...	XXX	XXX	XXX	XXX	XXX
Two lines	Line 1 Regimen ==> Line 2 Regimen	XXX	XXX	XXX	XXX	XXX
	Line 1 Regimen ==> Line 2 Regimen	XXX	XXX	XXX	XXX	XXX
	Line 1 Regimen ==> Line 2 Regimen	XXX	XXX	XXX	XXX	XXX
	...	XXX	XXX	XXX	XXX	XXX

PFIZER CONFIDENTIAL

Three lines	Line 1 Regimen ==> Line 2 Regimen ==> Line 3 Regimen	xxx	xxx	xxx	xxx	xxx
	Line 1 Regimen ==> Line 2 Regimen ==> Line 3 Regimen	xxx	xxx	xxx	xxx	xxx
	Line 1 Regimen ==> Line 2 Regimen ==> Line 3 Regimen	xxx	xxx	xxx	xxx	xxx
	...	xxx	xxx	xxx	xxx	xxx

Lines of therapy are progression-based and are restricted to the first 3 lines.

Table 4b. Summary of Treatment Sequencing Duration – Palbociclib + AI Patients

Repeat Table 4a for patients receiving Palbociclib with AI as initial endocrine-based therapy.

CCI

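### SAP 5.2 closes ongoing treatment at data cutoff and pools it with completed durations, so Tables 3a, 4a and 5a do not give time on treatment; the two dosing times have no censoring rule

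*SAP*

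**What the plan says.** SAP 5.2 ends a drug still being taken at data cutoff: "For ongoing treatment, the end date is the data cutoff date". For regimen and sequence durations it says: "For ongoing regimen, the end date is the data cutoff date". Neither sentence calls this censoring.

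The SAP Appendix 1 shells titled "Table 3a. Summary of Treatment Regimen Duration" and "Table 4a. Summary of Treatment Sequencing Duration" show n, percentage, mean, SD and median, with no count of ongoing patients. Table 5a gives mean, range, quartiles, median and month bands for palbociclib duration in one column. It counts ongoing and discontinued patients in a separate row but does not separate their durations.

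Time to Dose Discontinuation is "Months from the start date to the discontinuation date of the treatment", and Time to First Dose Adjustment is "Months from the start date to the first adjustment date of the treatment". Neither has a rule for patients without the event. SAP 6 adds "No imputation for missing values will be performed", and Table 5a has a row for the number of missing values. The types of dose adjustment are "Dose Modification; Schedule Changes; Dose Delay; Hold; Discontinuation".

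SAP 7.1 promises a Kaplan-Meier curve for each time-to-event outcome. The list in SAP 7.2 includes duration of initial endocrine-based treatment and duration of all treatment (Figures 3 and 4), but no variable from SAP 5.2.

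**The concern.** A duration closed at cutoff is a lower bound on time on treatment, not a completed time. Averaging it with completed times gives a figure that changes with the date on which curation ends, and SAP 5 gives no calendar date for that. Tables 6a, 7a, 10a and 11a carry a censored count and a Kaplan-Meier row, so the SAP uses censoring elsewhere and leaves it out here.

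The two dosing times have a different problem. With no rule for patients without the event, no imputation and a plain mean and median, the natural programming keeps only patients who had the event. Early events are then over-represented.

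Time to dose adjustment or discontinuation is named in primary objective 1b (protocol section 8, SAP 2.2). Among the displays that are visible, Table 5a is the only one for these palbociclib results. Regimen distribution, order, doses and reasons are not affected.

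**Working it through.** **The plan's own figure.** Protocol 9.5 gives average follow-up as 50/2 + 8 = 33 months. From the calendar dates it is 49.87/2 + 8.02 = 32.95, so the figure reproduces.

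**Inputs.**
- Starts are uniform over the 50-month window (2/3/2015 to 4/1/2019).
- Shortest potential follow-up F is 8 months (cutoff 12/1/2019) to 20 months (12 months later). The length of curation is not given, so the upper end is an assumption.
- Time on treatment is assumed exponential, with no loss to follow-up.
- The documents give no treatment-duration figure. The 24.5-month median PFS cited in protocol section 7 is a stand-in; 18 and 12 are alternatives.

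**Formulas.** With true median m:
- λ = 0.693/m and S(t) = exp(−λt).
- G(t), the share with potential follow-up beyond t, is 1 up to F and (50 + F − t)/50 after it.
- A pooled duration exceeds t with probability S(t)G(t). The plain median solves S(t)G(t) = 0.5, and the plain mean is the integral of S(t)G(t).
- The discontinued-only median is the median of the density proportional to λS(t)G(t).

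**Example, m = 24.5 (λ = 0.0283).**
- F = 8: at t = 17.3, S = 0.613 and G = (58 − 17.3)/50 = 0.814; the product is 0.50.
- F = 20: at t = 22.6, S = 0.528 and G = (70 − 22.6)/50 = 0.948; the product is 0.50.
- Share above 36 months: the true value is 0.36. As tabulated it is 0.36 × 22/50 = 0.16 to 0.36 × 34/50 = 0.25.

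**Results in months, F = 8 to F = 20.**

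| True median | True mean | Plain median | Plain mean | Discontinued-only median |
|---|---|---|---|---|
| 24.5 | 35.3 | 17.3–22.6 | 20.3–24.6 | 12.1–15.1 |
| 18 | 26.0 | 14.4–18.0 | 17.5–20.6 | 10.8–13.1 |
| 12 | 17.3 | 10.9–12.0 | 13.7–15.5 | 8.8–10.3 |

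The plain median is correct once every patient's potential follow-up exceeds the true median (18 and 12 at F = 20). The plain mean and the discontinued-only median are short in every row.

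**Does Kaplan-Meier repair it?** In 1,000 simulated datasets of 1,200 patients (m = 24.5, F = 8, no loss), the plain median averaged 17.3 (95% range 16.2–18.3). The Kaplan-Meier median averaged 24.5 (22.5–26.8). Table 4a is different, because its rows are defined by the lines a patient later reaches. With a true line-1 median of 18, and 50% or 70% of those ending line 1 moving to line 2 (assumed), Kaplan-Meier in the one-line row gave 26.4 or 39.8.

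**Time to first adjustment.** Assume a median of 12 to adjustment and 24.5 to discontinuation. The hazards are 0.0578 and 0.0283. The event-only median is 6.8 to 7.6.
- If discontinuation counts as an adjustment, the true median is 0.693/(0.0578 + 0.0283) = 8.1, a gap of 0.5 to 1.3 months.
- If it does not, the comparison is 12.0 (discontinuation censored) or 15.9 (the time by which half of all treated patients have an adjustment, with discontinuation competing).

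**The case against.** The tables are descriptive, the SAP tests no hypothesis, and the cutoff rule is stated openly. Table 5a shows how many patients are ongoing. Kaplan-Meier duration of initial endocrine-based treatment and of all treatment is already planned for objective 1b, and the general sentence in SAP 7.1 could be read to cover the two dosing times. All of this is true, and it narrows the point. It does not supply an estimate for palbociclib itself or by regimen and line. The SAP 7.1 sentence is not carried into the SAP 7.2 list, Table 5a or the visible figures, and no censoring date is given for the dosing times.

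Three stronger readings are tempting but not supported:
- *All these durations read short.* If patients lost to follow-up are carried to cutoff, their durations are too long. The documents give no loss rate. Protocol 9.3.4 derives treatment dates only through the end of the record or of the study, whichever is first, so whether such patients would be carried to cutoff is itself unclear.
- *The SAP prescribes an event-only analysis of the dosing times.* It does not say so; this is inferred from the definitions, SAP 6 and the shell.
- *Time to first adjustment is badly wrong.* SAP 5.2 lists discontinuation as a type of adjustment, and both statements of objective 1b place it there too. On that reading the illustrated gap is only 0.5 to 1.3 months; larger gaps need the other reading.

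**Conclusion.** The point holds for Tables 3a, 4a and 5a, their repeats, and the two dosing times. Followed as written, the plain summaries depend on the cutoff date and are not time on treatment. Without loss to follow-up, the plain-median error runs from none to about 7 months (24.5 − 17.3 = 7.2) over the cases tried. The event-only median is short in all of them. These sizes rest on exponential times, uniform starts, an assumed cutoff range and a PFS median used as a stand-in. That median is not an upper limit for time on the drug, because protocol 9.3.1 allows treatment through progression. No size is claimed for lines 2 and 3 or for duration of all treatment. This should be fixed before the tables are programmed, but it does not undermine the rest of objective 1b.

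**What to change.** (a) In Tables 3 and 5a, add Kaplan-Meier medians with 95% CIs and numbers of events and censored patients. The event is end of regimen or drug, including death on treatment. If, say, 10% of endings were deaths and were censored instead, a median of 24.5 would read 24.5/0.9 = 27.2. Censor patients alive without a documented end at end of record or last visit, no later than cutoff, in all lines. SAP 5.3 uses a last visit date only for patients with one line, and protocol 9.3.2 to 9.3.4 list no such date, so add it as a derived variable. Reconcile the SAP 5.2 cutoff rule with the end-of-record limit in protocol 9.3.4.

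(b) Analyse time to discontinuation and time to first adjustment by Kaplan-Meier in all treated patients, and add both to the SAP 7.2 list. State whether discontinuation counts as an adjustment. If it does not, treat discontinuation and death as competing events and report cumulative incidence.

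(c) Do not apply Kaplan-Meier to Table 4a rows. Label these rows, and any plain summaries or month bands kept in Tables 3 and 5a, as duration with ongoing treatment closed at the stated end date, not time to discontinuation. Add the number ongoing to Tables 3 and 4.

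(d) As a separate wording repair in SAP 5.3, duration of all treatment censors only patients still on the initial therapy; extend this to patients still receiving any line. Duration of initial endocrine-based treatment states no censoring rule; add the matching sentence.

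The cost is SAP wording, shell edits, minor programming and one derived date. Some small regimen-by-line cells may not reach a median.

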16. ECOG/performance status, if available or indication of impaired performance status not otherwise classified as an ECOG rating, at index date (± 60 days). Where available, Karnofsky performance status will be converted to corresponding ECOG score.
17. Comorbidities, indicated as present vs. not indicated as present at index date. The conditions and date of the condition to be assessed will include those assessed as part of the standard Charlson Comorbidity Index. These include myocardial infarction, congestive heart failure, peripheral vascular disease, cerebrovascular accident, hemiplegia, chronic obstructive pulmonary disease, ulcer disease, diabetes, renal disease, connective tissue disease such as rheumatoid arthritis or lupus, Alzheimer's or other dementia, cirrhosis or other serious liver disease, leukemia, lymphoma, metastatic solid tumor (other than breast cancer), and HIV/AIDS.

PFIZER CONFIDENTIAL

18. Other comorbidities of interest, indicated as present vs. not indicated as present at index date: hypertension and hyperlipidemia.
19. Dates of disease progression after index date through the end of the record or the end of the study, whichever occurs first.
20. Documentation of treatment modifications (dose modification, schedule changes, dose delay, hold, or discontinuation) for palbociclib, **CCI** [REDACTED] and reasons for treatment modifications, if applicable, from the index date through the end of the record or the end of the study, whichever occurs first. Date of treatment modification and reason for modification will be collected, if available.
 - Reasons for modification will include: Cost, disease progression, patient refusal/request, toxicity (specify), other (specify), or UD.
21. Oral anti-cancer therapies. This will include all treatments from the index date through the end of the record or the end of the study, whichever occurs first. **CCI** [REDACTED]
22. Documentation of any IV, IM, or subcutaneous anti-cancer therapy not otherwise documented in standard medication tables, including all treatments received from the index date through the end of the record or the end of the study, whichever occurs first. Agent and start and end dates will be collected.

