2.2. Study Objectives

Primary Objectives:

1. All Eligible Patients:

a. Describe demographic and clinical characteristics.

- *Demographic characteristics will include age, sex, race, insurance status, menopausal status, and region of residence at A/MBC diagnosis.*
- *Clinical characteristics will include stage of initial diagnosis, histology, Eastern Cooperative Oncology Group (ECOG) performance status (where available, Karnofsky performance status will be converted to corresponding ECOG score) and comorbid disease burden, HER2 and Estrogen receptor (ER)/ Progesterone receptor (PR) status, number and sites of distant metastasis at A/MBC diagnosis (if applicable); modalities of treatment received prior to A/MBC diagnosis (chemotherapy, hormone therapy, surgery, radiation therapy) and disease free interval (time between completion of adjuvant therapy and diagnosis of A/MBC).*

b. Describe treatment patterns.

- *Distribution of regimens from the diagnosis of A/MBC through the end of the record.*
- *Sequence of regimens across lines, through the end of the record of systemic therapy.*
- *Description of the dosing employed with administration of palbociclib, ribociclib, and abemaciclib. Description of the dosing will include the starting dose, end dose, dose adjustment (dose increase and dose reduction), reasons for dose adjustment (dose modification, schedule changes, dose delay, hold, or discontinuation), discontinuation, reason, and time to dose adjustment (discontinuation).*

2. *Among patients receiving Palbociclib + AI as initial endocrine-based therapy, examine clinical effectiveness outcomes including:*
 - a. *Real-world progression-free survival (rwPFS) will be assessed for the initial endocrine-based therapy.*
 - b. *Overall survival (OS) will be assessed from start of the initial endocrine-based therapy.*
 - c. *Real-world tumor response (rwTR) will be assessed as best overall response for each regimen received within the initial endocrine-based therapy.*

CCI [REDACTED]

[REDACTED]

[REDACTED]

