Repeat Table 4a for patients receiving Abemaciclib with AI as initial endocrine-based therapy.

Table 5a. Palbociclib Dosing Information

	Palbociclib (N=)
Starting Dose, n (%)	
Dose level 1	
Dose level 2	
Dose level 3	
End Dose, n (%)	
Dose level 1	
Dose level 2	
Dose level 3	
Palbociclib Treatment Status, n (%)	
Treatment Ongoing	
Treatment Discontinued	
Duration of Palbociclib Treatment (months)	
Mean/SD	
N/Missing Values	
Min/Max	
First Quartile/Third Quartile	
Median/IQR	
Duration of Palbociclib Treatment (months)	
<6	

PFIZER CONFIDENTIAL

6 – 12 13 – 24 25 – 36 >36	
Reason for Discontinuing Palbociclib Therapy, n (%) Cost Disease Progression Patient Refusal/Request Toxicity, specify Other, specify Undocumented	
Time to Dose Discontinuation Mean/SD N/Missing Values Min/Max First Quartile/Third Quartile Median/IQR	
Dose Adjustments, n (%) Dose Reduced 125mg – 100mg 125mg – 75mg 100mg – 75mg Dose Increased 75mg – 100mg 75mg – 125mg 100mg – 125mg	
Number of Patients Starting at 125 mg, n (%) Dose Reduced, n (%) ^a	
Type of Dose Adjustments Dose Modification Schedule Changes Dose Delay Hold Discontinuation	
Time to First Dose Adjustment Mean/SD N/Missing Values Min/Max First Quartile/Third Quartile Median/IQR	

^a Percentage is based on number of patients who start at 125 mg of Palbociclib.

[figure not shown]

Table 6a. Summary of Real-world Progression-free Survival – All Eligible Patients

	All Eligible Patients (N=)
Number of Real-world Progression Events, n (%)	
Number Censored, n (%)	
Kaplan-Meier Estimates of Time to Event (months)	
Median (95% CI)	

PFIZER CONFIDENTIAL

Table 6b. Summary of Real-world Progression-free Survival - Palbociclib + AI Patients

Repeat Table 6a for patients receiving Palbociclib with AI as initial endocrine-based therapy.

CCI

[figure not shown]

Table 7a. Summary of Overall Survival – All Eligible Patients

	All Eligible Patients (N=)
Number of All-cause Mortality, n (%)	
Number Censored, n (%)	
Kaplan-Meier Estimates of Time to Event (months)	
Median (95% CI)	

Table 7b. Summary of Overall Survival - Palbociclib + AI Patients

Repeat Table 7a for patients receiving Palbociclib with AI as initial endocrine-based therapy.

CCI

Table 8a. Summary of Real-world Tumor Response – All Eligible Patients

	All Eligible Patients (N=) n (%)
Regimenx	
Complete Response	
Partial Response	
Stable Disease	
Progressive Disease	
Not Evaluable	
Undocumented	
Regimeny	
Complete Response	
Partial Response	
Stable Disease	

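### Objective 1b asks why doses were adjusted and the reasons are to be curated, but SAP 5.2 and Table 5a report a reason only for stopping palbociclib

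*SAP*

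**What the plan says.** **Objective.** Objective 1b is a primary objective, worded alike in Protocol 8 and SAP 2.2. Its dosing item includes "reasons for dose adjustment (dose modification, schedule changes, dose delay, hold, or discontinuation), discontinuation, reason, and time to dose adjustment (discontinuation"). The reasons for adjustment and the reason for discontinuation are separate entries. The bracket after the first entry lists kinds of adjustment, not reasons.

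**Data collection.** Protocol 9.3.2, item 20, calls for "Documentation of treatment modifications (dose modification, schedule changes, dose delay, hold, or discontinuation) for palbociclib", with date and reason where these can be found. The codes are given once for all modification types: "Reasons for modification will include: Cost, disease progression, patient refusal/request, toxicity (specify), other (specify), or UD".

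**Analysis variables.** SAP 5.2 has one reason variable, for discontinuing treatment: "Cost; Disease Progression; Patient Refusal/Request; Toxicity, specify; Death, Other, specify, Undocumented". Adjustments have a type variable ("Dose Modification; Schedule Changes; Dose Delay; Hold; Discontinuation") and a time variable ("Months from the start date to the first adjustment date of the treatment"). No variable holds the reason for an adjustment.

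**Output.** The palbociclib shell, Table 5a in SAP Appendix 1, follows the same pattern. Its only reason block is "Reason for Discontinuing Palbociclib Therapy, n (%) Cost Disease Progression Patient Refusal/Request Toxicity, specify Other, specify Undocumented". It also tabulates reductions and increases by dose step, reductions among patients who started at 125 mg, type of adjustment, and time to first adjustment.

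**The concern.** A programmer who follows SAP 5.2 and Table 5a exactly will produce no output for one named element of a primary objective. In Table 5a, a patient reduced from 125 mg to 100 mg because of toxicity and a patient reduced because of cost fall in the same rows. The reader learns how often, in what way and when palbociclib dosing was changed, but not why, unless the patient stopped.

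Nothing else that can be read in the SAP fills the gap. SAP 7.2.1 plans no safety analyses. Protocol 11.2 sends individual, explicitly attributed adverse events to the sponsor's safety function, which is case reporting and not a study result.

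The time variable adds a smaller difficulty. SAP 5.2 counts discontinuation among the types of adjustment. If a discontinuation can be the first adjustment, time to first adjustment may pool stops for progression with holds for toxicity, and no planned breakdown by reason would separate them.

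**Working it through.** No sample size, power or error rate is involved, so the check is a side-by-side reading of what is curated and what is reported. The inputs are Protocol 9.3.2 item 20, SAP 5.2 and the readable rows of Table 5a.

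| Modification type | Reason curated (item 20) | Row by type (Table 5a) | Reason reported (SAP 5.2, Table 5a) |
|---|---|---|---|
| Dose modification | Yes, if available | Yes, plus dose steps | No |
| Schedule change | Yes, if available | Yes | No |
| Dose delay | Yes, if available | Yes | No |
| Hold | Yes, if available | Yes | No |
| Discontinuation | Yes, if available | Yes | Yes |

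**Tally.** Reasons are curated for 5 types and reported for 1. That leaves 5 − 1 = 4 of 5 types with a count but no reason.

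**Does redaction explain it?** Not for palbociclib. The rows of Table 5a are legible from starting dose to time to first adjustment, and the redaction marks in SAP 5.2 fall where other agents would be named. The dosing tables for the other agents cannot be read, so nothing is claimed about them.

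**Did the SAP drop the element on purpose?** Protocol 9.7 lets the SAP modify the protocol's plans, but SAP 2.2 repeats Objective 1b unchanged and no readable text says these reasons will not be analysed. A likelier explanation is the bracket in Objective 1b. It puts types where reasons belong, and SAP 5.2 appears to have implemented the bracket as its type variable.

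**Can the loss be sized?** The documents give no frequency for any adjustment or reason. To see how far a figure would depend on assumptions, suppose that 30–50% of palbociclib patients have a reduction, hold or delay and that 5–15% stop for toxicity. These rates are illustrative and do not come from the documents. Let U be the share of patients with any toxicity-driven change whose toxicity reason appears in no row of Table 5a:

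- 50% adjusted, all for toxicity; a further 5% stop for toxicity; no overlap: U = 50 / (50 + 5) = 91%.
- 30% adjusted, all for toxicity; a further 15% stop for toxicity; no overlap: U = 30 / (30 + 15) = 67%.
- 30% adjusted, all for toxicity; 15% stop for toxicity, all adjusted first: U = (30 − 15) / 30 = 50%.
- 30% adjusted, 51% of these for toxicity (15.3%); 15% stop for toxicity, all of them among those 15.3%: U = (15.3 − 15) / 15.3 = 2%.

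A range of 2% to 91% shows that no useful size can be given.

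**The case against.** **The objective is ambiguous.** Objective 1b qualifies its reasons with a list of types, and SAP 5.2 can be read as following that text item by item: doses, types, reason for discontinuing, times. This stands as an account of how the gap arose. It does not close it, because types are not reasons, the reason for discontinuation is listed separately, and item 20 shows that reasons were meant to be collected for every type.

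**The data may be thin.** Item 20 collects date and reason only where available, and undocumented is one of its codes. This stands: some of the new table will be undocumented, and that share should be shown.

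**The study is descriptive and makes no tolerability claim.** SAP 3.1 has no hypotheses, no readable objective concerns safety, and no effectiveness estimate moves. This also stands and limits the weight of the point. The reason for an adjustment still belongs to treatment patterns, which Objective 1b covers.

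**A stronger reading to avoid.** A reader might infer that most of the study's tolerability information never reaches a result. The documents do not support this. Table 5a reports the frequency, type and timing of adjustments, the dose steps, and toxicity as a reason for discontinuation. Only the reason attached to the other four types is missing. Four of five types is not a share of patients or records. Nor can one say that no planned table anywhere gives these reasons, because the other agents' dosing tables and further objective text are redacted.

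**Conclusion.** The gap is real for palbociclib and is confined to the reasons for adjustments short of discontinuation. Reasons are to be curated for five modification types and reported for one. As written, the study cannot say why palbociclib doses were modified, schedules changed, or treatment delayed or held, although a primary objective names this.

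The conclusion rests on the readable text of SAP 5.2 and Table 5a, and on reading the reasons in Objective 1b as reasons, which item 20 supports. No number of patients can be attached to it. rwPFS, OS and rwTR are unaffected. It should be corrected before the tables are programmed, because a named element of a primary objective would otherwise go unanswered while the data to answer it are being collected.

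**What to change.** 1. In SAP 5.2, add a variable for the reason for dose adjustment, using the item 20 codes, including toxicity with the term specified and undocumented.
2. In Table 5a, add a type-by-reason block: number and percentage of palbociclib patients with at least one adjustment of each non-discontinuation type, by reason. Use palbociclib-treated patients as the denominator, let a patient count under more than one reason, and show the undocumented row.
3. State in the SAP that the bracket in Objective 1b lists types of adjustment and that reasons are reported separately. Correct the protocol wording at the next amendment; Protocol 10.3 requires ethics approval for amendments, so this need not be a separate submission.
4. In the same edit, reconcile the discontinuation codes: SAP 5.2 includes death, but Table 5a and item 20 do not.

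If the sponsor does not intend to analyse these reasons, the SAP should say so and the objective should be amended to match.

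The cost is one variable and one table block from data already due to be curated. The downside is that some reasons will be undocumented.

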8. RESEARCH QUESTION AND OBJECTIVES

The objective of this study is to describe the patient characteristics, treatment patterns, and clinical effectiveness outcomes for patients with a diagnosis of HR+/HER2- A/MBC who received CDK4/6i combination therapy with AI as the initial endocrine-based therapy in the A/MBC setting.

Primary Objectives:

1. Among patients with HR+/HER2- A/MBC receiving CDK4/6i combination therapy with AI as initial endocrine-based therapy:
 - a. Describe demographic and clinical characteristics.
 - Demographic characteristics will include age, sex, race, insurance status, menopausal status, and region of residence at A/MBC diagnosis;
 - Clinical characteristics will include stage of initial diagnosis, histology, Eastern Cooperative Oncology Group (ECOG) performance status (where available, Karnofsky performance status will be converted to corresponding ECOG score) and comorbid disease burden, HER2 and Estrogen receptor (ER)/Progesterone receptor (PR) status, number and sites of distant metastasis at A/MBC diagnosis (if applicable); modalities of treatment received prior to A/MBC diagnosis (chemotherapy, hormone therapy, surgery, radiation therapy) and disease free interval (time between completion of adjuvant therapy and diagnosis of A/MBC).
 - b. Describe treatment patterns.
 - Distribution of regimens from the diagnosis of A/MBC through the end of the record;

- Sequence of regimens across lines, through the end of the record of systemic therapy;
- Description of the dosing employed with administration of palbociclib, ribociclib, and abemaciclib. Description of the dosing will include the starting dose, end dose, dose adjustment (dose increase and dose reduction), reasons for dose adjustment (dose modification, schedule changes, dose delay, hold, or discontinuation), discontinuation, reason, and time to dose adjustment (discontinuation).

2. Among patients receiving Palbociclib + AI as initial endocrine-based therapy, examine clinical effectiveness outcomes including:
 - a. Real-world progression-free survival (rwPFS) will be assessed for the first endocrine-based therapy.
 - b. Overall survival (OS) will be assessed from start of the first endocrine-based therapy.
 - c. Real-world tumor response (rwTR) will be assessed as best overall response for each regimen received within the first endocrine-based therapy.

CCI [REDACTED]

[REDACTED]

[REDACTED]

[REDACTED]

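### Time to First Dose Adjustment counts stopping treatment as a dose adjustment, so it mixes discontinuation with dose changes, to an extent the documents do not let one quantify

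*SAP*

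**What the plan says.** SAP 5.2 gives the types of dose adjustment as "Dose Modification; Schedule Changes; Dose Delay; Hold; Discontinuation". The next row, Time to First Dose Adjustment, is "Months from the start date to the first adjustment date of the treatment". Two other rows of the same table deal with stopping: Time to Dose Discontinuation, "Months from the start date to the discontinuation date of the treatment", and the reasons for discontinuing, "Cost; Disease Progression; Patient Refusal/Request; Toxicity, specify; Death, Other, specify, Undocumented".

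Table 5a (SAP Appendix 1) repeats the five types and follows them with a single row block, "Time to First Dose Adjustment", summarised by mean, SD, range and quartiles. A separate block in the same table, headed Dose Adjustments, contains only reductions and increases.

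Objective 1b (Protocol 8, repeated in SAP 2.2) reads "dose adjustment (dose increase and dose reduction), reasons for dose adjustment (dose modification, schedule changes, dose delay, hold, or discontinuation", then names discontinuation again as its own item and ends with "time to dose adjustment (discontinuation" in parentheses. Protocol 9.3.2 item 20 collects the same five components under a broader label, treatment modifications, with date and reason where available.

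**The concern.** The time row has a mixed event. A reduction, a short delay and the end of treatment all count alike, and whichever comes first sets the time. A patient with no dose change who stops at month 20 enters as a dose adjustment at month 20.

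Time to dose adjustment is a named item of primary objective 1b, and a reader will take it to show when doses were changed. Under the stated rule it also reflects how long unadjusted patients stayed on drug, so longer treatment without a dose change can lengthen the reported time. The number of patients behind the row need not match the count under Dose Adjustments in the same table, and two programmers could produce different results while each following the SAP. Adding a censoring rule would not cure this, because the event itself is mixed.

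**Working it through.** **Step 1: the text.** The term carries different meanings in different places.

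| Place | What counts as dose adjustment |
|---|---|
| Objective 1b, opening words | Increase and reduction |
| Table 5a, Dose Adjustments | Reduction and increase |
| SAP 5.2 and Table 5a, Type of Dose Adjustments | Five types, including discontinuation |
| Objective 1b, closing words | Adjustment and discontinuation run together |
| Protocol 9.3.2 item 20 | Same five components, but called treatment modifications |

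In both SAP 5.2 and Table 5a the time row comes directly after the five-type list, so the five-type reading is the natural one. For any patient whose only recorded adjustment is stopping, Time to First Dose Adjustment equals Time to Dose Discontinuation.

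**Step 2: the plan's own figures.** The documents give no expected rate of adjustments or discontinuations, so there is no stated figure for this endpoint to reproduce. The only related arithmetic is average follow-up in Protocol 9.5: 50/2 + 8 = 33 months, which is correct.

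**Step 3: an illustration of the size.** Inputs:

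- Cutoff uniform over 8 to 58 months after start (the 50-month window plus 8 months in Protocol 9.5).
- Stopping is exponential and assumed to follow the progression-free figures in Protocol 7. Proxy A is the 24.5-month median: h = ln 2/24.5 = 0.0283 per month. Proxy B is 84.1% progression-free at 12 months: h = −ln(0.841)/12 = 0.0144 per month.
- A fraction p of patients is prone to some other adjustment, exponential with median m and a = ln 2/m. Neither p nor m is in the documents; I take p from 10% to 80% and m from 3 to 12 months.

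With F(k) = 1 − (e^(−8k) − e^(−58k))/(50k), the chance that an event with rate k occurs before cutoff:

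- Other adjustment first: O = p × a/(a+h) × F(a+h)
- Discontinuation first: D = p × h/(a+h) × F(a+h) + (1−p) × F(h)
- Share of first adjustments that are stops = D/(D+O)

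Worked case, proxy A, p = 30%, m = 6: a = 0.1155, F(a+h) = 0.956, F(h) = 0.573. O = 0.3 × 0.803 × 0.956 = 0.230. D = 0.3 × 0.197 × 0.956 + 0.7 × 0.573 = 0.458. Share = 0.458/0.688 = 67%.

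Across m = 3 to 12 months:

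| p | Proxy A | Proxy B |
|---|---|---|
| 10% | 86–90% | 78–84% |
| 30% | 62–73% | 49–60% |
| 50% | 44–59% | 31–44% |
| 70% | 29–47% | 19–32% |
| 80% | 22–42% | 14–28% |

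A slightly earlier onset (mean 4 months, so median 4 × ln 2 = 2.8) with proxy B and p = 80% gives 13%. The overall range is therefore about 13–90%.

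**Step 4: effect on the reported time.** In a simulation of 400,000 patients for the worked case, the median among patients with an observed event is 7.9 months when discontinuation counts and 4.5 months for the other adjustments alone.

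**The case against.** The strongest objection is that the SAP follows the protocol. Objective 1b itself ends by coupling dose adjustment with discontinuation and puts discontinuation in the list attached to adjustment, so no clear narrow definition has been breached. That stands: the ambiguity starts in the protocol, and both documents need attention. It does not rescue the endpoint, because the same sentence also gives the narrow meaning.

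A second objection is that SAP 5.2 never says the time row uses the five-type list. That is literally true, but the list is the only account of adjustment types in SAP 5.2 and no type is excluded.

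A third is that stopping is already visible: types are tabulated, discontinuation has its own status, reason and time rows, and the study tests no hypotheses. This limits the harm. It does not let a reader separate the pooled time row, which nothing in the shell splits by type.

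A reader might go further and infer that the row will largely measure stopping, often for progression. The documents do not support this. They give no adjustment rates and no share of discontinuations due to progression. Because the row takes the first event, an earlier delay, hold, schedule change or dose change displaces a later stop. Modelling reductions alone (20–40% of patients prone, mean onset 4 months, median time to stopping 15–24.5 months) gives 52–79% stops, but that omits the other adjustment types, and the 15-month figure is not in the documents.

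**Conclusion.** The point holds as a definition problem. The stated rule counts a stop on an unchanged dose as a dose adjustment, duplicates Time to Dose Discontinuation for those patients, and conflicts with the increase-and-reduction meaning used elsewhere. The affected patients are those who stop with no earlier recorded adjustment.

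Their share cannot be derived. The 13–90% range rests on assumed exponential times, on stopping following progression-free survival, and on adjustment rates chosen only to span a wide range. Within the tabulated onset range, stops exceed half of first adjustments in every scenario only when about 20% of patients or fewer are prone to another adjustment, and fall below half in every scenario at 70% or more. It is worth correcting before analysis because the item belongs to a primary objective and the correction is cheap. It concerns reporting only and implies no change to any dosing or stopping decision.

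**What to change.** 1. In SAP 5.2 and Table 5a, remove Discontinuation from Type of Dose Adjustments and from the event in Time to First Dose Adjustment. Alternatively, retitle the five-item list treatment modifications, as in Protocol 9.3.2 item 20, and state that the time row excludes discontinuation.
2. Report the number of patients with a non-discontinuation adjustment and the time to the first one. Use cumulative incidence, with discontinuation or death before any adjustment as a competing event and censoring at data cutoff.
3. Keep discontinuation in its existing status, reason and time rows.
4. Reconcile the wording of objective 1b in Protocol 8 and SAP 2.2, including its closing parenthesis, so that the term has one meaning throughout.

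A separate time to first dose reduction would be an optional addition; the defect does not require it.

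The cost is a minor wording change in both documents, one revised table shell, and an estimator in place of simple summary statistics. Type and date of modification are already to be curated where available, so no new data are needed. The downside is fewer events behind the row.
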